1.0 BACKGROUND AND RATIONALE

1.1 Study Synopsis

This is a randomized double-blind controlled trial in participants undergoing allogeneic hematopoietic stem cell transplantation (HSCT) to determine if high dose intravenous (IV) thiamine can prevent delirium and minimize the deleterious impact of delirium on health-related quality of life (HRQOL), functional status, and other neuropsychiatric outcomes. We will recruit 60 evaluable patients scheduled for allogeneic HSCT at UNC, randomize them to treatment with high dose IV thiamine (n = 30) versus placebo (n = 30), and systematically evaluate all participants for delirium and related comorbidities. We will use the Delirium Rating Scale (DRS) to measure the severity and duration of delirium immediately prior to transplant and after HSCT until 30 days post-transplant or discharge. We will obtain thiamine levels and other laboratory parameters associated with delirium the day after transplant, and continue to monitor thiamine levels weekly thereafter. We will also monitor HRQOL (FACT-BMT), functional status (ECOG-PS), depression (PROMIS-D), post-traumatic stress symptoms (PTSS-14), and cognitive function (MOCA) prior to transplant and at one, three, and six months after transplant to elucidate the persistent impact of delirium in this population and the potential for thiamine to mitigate these negative outcomes.

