2.2 Secondary Objectives

2.2.1 To compare delirium severity between recipients of high dose IV thiamine and placebo during hospitalization for allogeneic HSCT.

2.2.2 To compare delirium duration between recipients of high dose IV thiamine and placebo during hospitalization for allogeneic HSCT.

2.2.3 To determine if thiamine status is predictive of subsequent delirium onset.

2.2.4 To investigate the effects of high dose IV thiamine on long-term health-related quality of life (HRQOL), functional status, depression, post-traumatic stress symptoms, and cognitive functioning in patients who undergo HSCT.

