3.0 Criteria for Evaluation / Study Endpoints

3.1 Primary Endpoint

Delirium incidence will be defined as: DRS > 12. Delirium rating scales will be performed at baseline (prior to transplant) and then three times weekly from day after transplant to 30 days after transplant or discharge, whichever comes first.

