3.2 Secondary Endpoints

3.2.1 Delirium duration will be measured in days and delirium severity will be defined as the highest DRS score recorded. If delirium occurs, frequency of assessment will increase to daily, Monday through Friday, as scheduling permits, until delirium resolves.

3.2.2 We will examine the relationship between thiamine levels at the end of the seven day intervention period and the development of delirium at any point during the post-transplant hospitalization.

3.2.3 Scores on FACT-BMT, PROMIS-D, PTSS-14, ECOG-PS, and MOCA will be measured at one, three, and six months after transplant.

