7.0 EVALUATIONS AND ASSESSMENTS

7.1 Time and Events Table

	Baseline (Pre- Transplant)	Post-Transplant Day 1	Post-Transplant Days 2 – 30	F1 ^c	F2	F3
Informed Consent	•					
Group Assignment	•					
Demographic Data Form	•					
Cancer History Form	•					
Delirium Risk Factor Form	•	•	•			
Concurrent CNS Active Medication Tracking Form	•	•	•			
Baseline Labs ^a		•				
Thiamine Levels ^b		•	•			
FACT-BMT ^c	•			•	•	•
PROMIS-D ^c	•			•	•	•
PTSS-14 ^c	•			•	•	•
MOCA ^c	•			•	•	•
ECOG-PS ^c	•			•	•	•
DRS ^d	•	•	•			
Adverse Events Form		•	•			

- a. Complete Blood Count (CBC), Comprehensive Metabolic Panel (CMP), Magnesium (Mg), Phosphorus (Phos)
- b. Thiamine levels will be drawn on post-transplant day 1, 8 days post-transplant, 15 days post-transplant, 22 days post-transplant, and 29 days post-transplant.
- c. FACT-BMT, PROMIS-D, PTSS-14, MOCA, and ECOG-PS will be performed at baseline (pre-transplant) and at one (F1), three (F2), and six months (F3) after transplant.
- d. DRS will be performed at baseline, on post-transplant day 1, and three times weekly thereafter. If a participant is identified as having delirium, assessments will increase to daily until delirium resolves at which point frequency will resume at three times weekly. For participants who develop delirium during the inpatient phase, DRS will be performed at one (F1), three (F2), and six months (F3) after transplant.

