7.4 Post-Transplant Days 1 – 30 Assessments

Within two days of transplant, the subject will have a CBC, CMP, Mg level, Phos level, and Thiamine level drawn. The CRA(s) or investigators will perform the delirium assessment (DRS), and a brief history will be obtained to assess for any toxicity from therapy.

Over the course of 30 days following transplant (or discharge, whichever comes first), the subject will continue to have weekly thiamine levels drawn (at days 8, 15, 22, and 29 +/- one day). The CRA(s) or investigators will continue to assess for delirium, using the DRS, three times weekly. If a subject is determined to

have delirium, frequency of delirium assessments will increase to daily, Monday through Friday, as scheduling permits, until delirium resolves. The DRS assessments will not be performed if a patient becomes unevaluable due to an acute medical concern (e.g. intubation, sedation, etc.). The CRA(s) or investigators will continue to assess for any toxicity from therapy.

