9.3 Data Analysis Plans

To compare delirium incidence, severity, and duration between recipients of high dose IV thiamine and placebo during hospitalization for HSCT. The primary outcome measure is delirium incidence, defined as: DRS > 12. Secondary outcomes are differences in delirium duration (in days) and delirium severity, in which higher DRS scores suggest more severe delirium. A two group chi-squared test will be used to compare rates of delirium in the intervention and control group. Maximum severity score will be analyzed using two group t-tests, and time to delirium will be compared between groups using the Kaplan-Meier

method. For those with delirium, two group t-tests will compare the duration of delirium between intervention groups; Kaplan-Meier methods may also be considered for time to delirium resolution.

To determine if thiamine status is predictive of future delirium onset. We will examine the relationship between thiamine levels at the end of the seven day administration of thiamine and the development of delirium at any point during the thirty days post-transplant or the post-transplant hospitalization, whichever comes first. Patients who develop delirium prior to the end of the thiamine treatment will not be included in this analysis. We will examine the sensitivity and specificity of this relationship with ROC curves, and attempt to find a cutoff for thiamine levels that is associated with the development of delirium.

To investigate the effects of high dose IV thiamine on long-term health-related quality of life (HRQOL), functional status, depression, post-traumatic stress symptoms, and cognitive functioning in patients hospitalized for HSCT. Scores on FACT-BMT, PROMIS-D, PTSS-14, ECOG-PS and MOCA will be compared between intervention and control groups. We will summarize scores on the FACT-BMT, PROMIS-D, PTSS-14, ECOG-PS, and MOCA between the intervention and control groups at one, three, and six months post-transplant. Longitudinal modeling will be performed to examine differences/changes over time.

Safety Analyses: We will tabulate AEs and SAEs, by treatment and placebo, within strata. We will include all AEs which occurred at a rate of more than 5% in any treatment.

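### Delirium duration is to be compared by t-test although some episodes may be unresolved at the last rating, so later onset alone could look like shorter delirium

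*Combined protocol and SAP*

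**What the plan says.** **When rating ends.** Section 1.1 plans to use the DRS to "measure the severity and duration of delirium immediately prior to transplant and after HSCT until 30 days post-transplant or discharge". Section 3.1 schedules ratings "three times weekly from day after transplant to 30 days after transplant or discharge, whichever comes first". Note d to the table in 7.1 says that, once delirium is found, "assessments will increase to daily until delirium resolves at which point frequency will resume at three times weekly". Sections 3.2.1 and 7.4 likewise have daily weekday ratings, as scheduling permits, until resolution. No section says whether this overrides the day-30 or discharge limit. Under 7.4, DRS is not done while a patient is unevaluable, for example intubated or sedated. Note d and 7.5 add a DRS at one, three and six months for patients who were delirious as inpatients.

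**What duration is.** Objective 2.2.2 is "To compare delirium duration between recipients of high dose IV thiamine and placebo during hospitalization for allogeneic HSCT". Section 3.2.1 says "Delirium duration will be measured in days and delirium severity will be defined as the highest DRS score recorded". It gives no rule for an episode that is unresolved at the last rating.

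**How it is analysed.** For patients with delirium, section 9.3 says "two group t-tests will compare the duration of delirium between intervention groups; Kaplan-Meier methods may also be considered for time to delirium resolution". The same section commits to Kaplan-Meier, without qualification, for time to delirium onset.

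**The concern.** An episode that is still open when rating ends has a known minimum length, not a known length. A two-group t-test on days has no means of marking it as open. What can be observed is limited by the time left between onset and the end of rating, so recorded duration depends on when delirium began as well as on how long it lasted.

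The trial aims at prevention, and study drug is given only on post-transplant days 1–7, so delayed onset is a plausible effect. If thiamine delayed delirium without shortening it, more thiamine episodes would be cut, and the comparison for objective 2.2.2 would show a benefit that is not there. An episode ended by death could also count as a short one, because the plan does not say how it is scored.

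**Working it through.** **1. The plan's own figure (section 9.2).** Inputs: 0.445 v 0.155, 30 per arm, one-sided 0.05. The pooled rate is 0.30.

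z = [0.29·√30 − 1.645·√(2·0.30·0.70)] / √(0.445·0.555 + 0.155·0.845) = (1.588 − 1.066)/0.615 = 0.85, so power is 80.2%.

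The stated 80% reproduces. No calculation is given for duration.

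**2. Size of the duration comparison.** 30 × 0.445 = 13.35 and 30 × 0.155 = 4.65, so about 13 v 5 delirious patients and 18 in all.

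**3. Bias from later onset alone.** These inputs are assumptions, not figures from the documents: exponential duration with the same mean m in both arms, placebo onset uniform over days 2–20, thiamine onset d days later, rating cut at day 30.

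- Share of episodes cut: p = (m/18)·[exp(−(10 − d)/m) − exp(−(28 − d)/m)]
- Mean observed duration: m·(1 − p)

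For m = 7 and d = 0: p = (7/18)·(0.2397 − 0.0183) = 0.086, and the mean is 7 × 0.914 = 6.40. For d = 5: p = (7/18)·(0.4895 − 0.0374) = 0.176, and the mean is 5.77.

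| True mean (days) | No delay | 5-day delay | 7-day delay | False shortening |
|---|---|---|---|---|
| 3 | 2.98 | 2.91 | 2.82 | 0.1–0.2 |
| 7 | 6.40 | 5.77 | 5.36 | 0.6–1.0 |
| 10 | 8.29 | 7.19 | 6.56 | 1.1–1.7 |

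For m = 7 the shares cut are 9%, 18% and 23%. If rating instead ends on day 25, with placebo onset on days 2–16 and m = 7, the means are 6.16, 5.29 and 4.73, a false shortening of 0.9–1.4 days. With no delay the arms agree.

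**4. Dropping unresolved episodes does not help.** This comes from a separate simulation with other assumptions: true mean 8 days in both arms, onset around day 10 (SD 4), an 8-day delay, discharge around day 25 (SD 4).

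- Entered at cut-off length: 6.4 v 4.6 days.
- Unresolved episodes dropped: 5.25 v 3.70 days.
- Censored estimates: 8.0 v 8.0 days.

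**5. Effect on the test, one-sided at nominal 5%.** Under the step 3 assumptions with m of 7 to 10 days and a 5- to 7-day delay, simulation gives the t-test a false-positive rate of about 5–9% with 13 v 5 delirious patients (about 4% with no delay at m = 7). With 13 per arm the rate is about 8–19%. Under the harsher step 4 assumptions, the t-test and log-rank rates are about 13% and 9% with 13 v 5, and about 27% and 6% with 13 per arm. With 13 v 5 and no delay, the log-rank rate is already about 8%.

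**The case against.** **The rating rule is not one-sided.** A reader might infer that rating simply stops in a patient who is still delirious. The documents do not support that: three places say it runs until resolution. The 30-day phrase in 7.4 is no counter-evidence, because its sentence is about thiamine draws. Intubation or sedation may only suspend rating. What stands is an unresolved conflict with 1.1 and 3.1.

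**The plan never says that cut-off lengths are used as true durations.** That too would be an inference, as would a fixed scoring of deaths. The plan is silent on both. But dropping unresolved episodes is biased in the same direction.

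**The measure may be delirium days in hospital.** Objective 2.2.2 can be read that way, and discharge then completes the measurement. This is fair, but such a measure still depends on onset time, and the plan should say so.

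**The size rests on assumed inputs.** No document predicts a delay of 5–7 days. For a mean of 7 days and a 5-day delay, the bias of 0.6 day is about 0.24 of a standard error (about 2.6 days) at 13 v 5, and the test is not materially inflated. This limits the point at the planned counts. It limits it less if the arms have similar numbers of delirious patients.

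**Later DRS visits exist.** Their windows run from ±2 weeks to ±2 months, too wide to give a duration in days.

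**Conclusion.** The point holds in a conditional form. The plan conflicts on when rating of a delirious patient ends, has no rule for unresolved episodes, commits to a test that cannot accommodate them, and leaves the suitable method optional. Where the day-30 or discharge limit applies and thiamine delays onset, delirium will look shorter than it is.

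The bias is negligible for episodes of about 3 days, about 0.6–1.0 day for a mean of 7 and 1.1–1.7 days for a mean of 10. These sizes rest on the assumed exponential durations, onset range, day-30 cut and delay. At the planned counts the false-positive rate rises only modestly; it rises more if delirium is about equally common in both arms. This concerns a secondary endpoint. The primary analysis and its stated power are unchanged.

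**What to change.** 1. Reconcile 1.1 and 3.1 with 3.2.1, 7.1 note d and 7.4, so that one rule says when rating of a delirious patient ends.
2. Record on the eCRF why each episode ended: resolution (DRS ≤ 12), discharge, day 30, loss of evaluability, or death.
3. In 9.3, make time to resolution the stated duration analysis in place of the t-test. Censor unresolved episodes at the last DRS and treat death as a competing event.
4. Use the one-month DRS only to confirm resolution, not to date it.
5. If delirium days in hospital is the intended measure, say so and state that it depends on onset time.

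The cost is mainly wording and one eCRF field, plus a few ratings of up to 10 minutes each if rating is to continue past day 30. The statistical downsides are less precision with about 18 delirious patients, a log-rank test that is slightly anti-conservative at that size, and censoring at discharge or intubation that may be informative. Discharge may follow recovery and intubation may follow deterioration, so a sensitivity analysis should be specified.

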7.11 Assessment of Efficacy

In order to be considered evaluable for efficacy, patients must:

- receive all 7 days of the treatment; a patient must receive at least 17/21 (80%) thiamine doses
- have delirium assessed at least weekly until one of the following is met:
 1. The participant is found to be delirious (DRS>12)
 2. The participant is at least 30 days post-transplant
 3. The participant is discharged

If a patient is deemed not evaluable, they will be replaced by a new patient. However, if a patient develops delirium during the intervention, they will still

receive the full 7 day course, not be replaced, and included in the efficacy analysis.

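### Section 9.3 starts the clock for subsequent delirium at the end of dosing, not at the blood draw, so a few onsets can precede the thiamine level said to predict them

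*Combined protocol and SAP*

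**What the plan says.** Objective 2.2.3 is "To determine if thiamine status is predictive of subsequent delirium onset". Section 9.3 puts this into practice in three parts:

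- Predictor: "thiamine levels at the end of the seven day administration of thiamine". No draw day is named.
- Outcome: "the development of delirium at any point during the thirty days post-transplant or the post-transplant hospitalization, whichever comes first".
- Exclusion: "Patients who develop delirium prior to the end of the thiamine treatment will not be included in this analysis". No analysis population is named.

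Endpoint 3.2.2 describes the same analysis as relating "thiamine levels at the end of the seven day intervention period and the development of delirium at any point during the post-transplant hospitalization". It carries no exclusion.

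The timing comes from other sections. The regimen table in 5.2 gives study drug three times daily on post-transplant days 1 to 7. Footnote b of the Time and Events Table (7.1) puts the second thiamine sample at 8 days after transplant, and section 7.4 adds a window: "weekly thiamine levels drawn (at days 8, 15, 22, and 29 +/- one day". Section 7.4 also sets DRS assessments at three per week, and section 5.9.1 says that each DRS rating covers a 24-hour period.

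**The concern.** A level can predict subsequent onset only if it was measured first. The exclusion in 9.3 is evidently meant to secure that order, but it is tied to the end of dosing and not to the sample. Take a patient who finishes dosing on day 7, first scores above 12 on day 8 and is sampled on day 9. That patient is not excluded, and counts as a delirium predicted by a level taken after onset. The mismatch exists on the nominal schedule too, since the last dosing day is day 7 and the planned draw is day 8. In the other direction, a patient sampled on day 7 and found delirious later that day, before the last dose, is dropped although the level came first.

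The order matters because section 1.2 attributes thiamine depletion to poor intake, infection and graft-versus-host disease. A level taken after onset may partly reflect illness that accompanied the delirium. The planned output is an ROC curve and a cutoff chosen from the data, and with few events one or two mis-ordered patients can move both. Section 1.5 also presents the temporal relationship between deficiency and delirium as a novel contribution of the design.

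**Working it through.** **1. Source of the event count.** The plan gives no event count or power for this analysis, so the count has to come from the primary sample size in 9.2: rates 0.445 and 0.155, 30 per arm, one-sided 0.05. With a normal approximation, pooled variance under the null and no continuity correction:

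z = [0.29 × √30 − 1.645 × √(2 × 0.30 × 0.70)] / √(0.445 × 0.555 + 0.155 × 0.845) = (1.588 − 1.066) / 0.615 = 0.85, so power = 80.2%.

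The stated 80% reproduces. It has no bearing on the timing question beyond supplying the rates.

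Expected delirium events = 30 × 0.445 + 30 × 0.155 = 13.35 + 4.65 = 18.

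**2. Gap between the end of dosing and the sample.**

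| Draw day | Gap after day 7 | Consequence under 9.3 |
|---|---|---|
| 7 | 0 days | no onset is wrongly kept; one between the sample and the last dose is wrongly dropped |
| 8 (planned) | 1 day | onset after the last dose and before the draw is kept |
| 9 | 2 days | as for day 8, with a longer gap |

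**3. Events in the gap.** The documents give no onset times, so each pattern below is an assumption. For onset spread evenly over H days:

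- events after day 7 = 18 × (H − 7) / H
- mis-ordered events = 18 × gap / H
- share = gap / (H − 7)

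These figures count the whole of the draw day as coming before the draw, so they lean high.

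| Assumed onset | Events after day 7 | All draws on day 8 | All draws on day 9 |
|---|---|---|---|
| Even over 30 days | 13.8 | 0.6 (4%) | 1.2 (9%) |
| Even over 21 days | 12.0 | 0.9 (7%) | 1.7 (14%) |
| Even over 14 days | 9.0 | 1.3 (14%) | 2.6 (29%) |

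Exponential onset with a mean of 7 to 14 days, truncated at day 30, gives about 0.9 events (9–14%) with day-8 draws and 1.7 (17–26%) with day-9 draws. With day-7 draws the number is zero under every pattern.

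**4. Weight of one event in the ROC curve.** The AUC is the average, over events, of the share of non-events each one is ranked against correctly. With 12 events (the 21-day row), one event carries at most 1/12 = 0.083. A shift of that size needs the event to move from one extreme rank to the other. If the other 11 events average 0.5 and one mis-ordered event ranks perfectly, the AUC is (11 × 0.5 + 1) / 12 = 0.542, a rise of about 0.04. From 0.7 it is (11 × 0.7 + 1) / 12 = 0.725, a rise of 0.025.

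**The case against.** The plan already excludes delirium that develops during treatment, which is the main threat to temporal order. What remains is a gap of a day or so. The analysis carries no alpha or power, and 9.1 does not list it among the secondary endpoints. The summary of Amendment 2 says the one-day window was added to catch patients discharged just before a planned draw. That points towards early draws, for which no onset is wrongly kept. Endpoint 3.2.2 is a brief statement that can be read together with 2.2.3 and 9.3. All of this limits the size of the problem. None of it closes the gap on the nominal day-7 to day-8 schedule, because no section ties the outcome period to the draw.

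Two further objections limit what a fix can do. Illness that lowers thiamine and also brings on delirium would distort a level drawn the day before onset as well, so restoring the order does not remove confounding by a common cause. And with three DRS assessments a week, onset is known only to within about two or three days. Both stand.

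A reader might infer that the gap is much wider in patients who stop early, for example a patient who stops on day 3, or one who reaches 17 doses on day 6. The documents do not support leaning on these cases. Section 7.11 asks for all seven days of treatment and adds that "a patient must receive at least 17/21 (80%) thiamine doses". A day-3 stopper has at most 9 of 21 doses, is not evaluable for efficacy and is replaced. Finishing on day 6 does not satisfy the seven-day clause, although 9.1 repeats only the 80% part. Section 9.3 names no population, but the only alternative that 9.1 defines is the Safety Population. The natural reading is therefore the common day 1 to 7 dosing period.

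**Conclusion.** The point holds as a small, correctable error in a secondary analysis. The rule in 9.3 does not deliver the temporal order that objective 2.2.3 requires, and 3.2.2 does not match 9.3. With even onset over 30 days, about 0.6 of 13.8 post-dosing events (4%) would be mis-ordered if patients are drawn on day 8, up to 1.2 (9%) if all are drawn on day 9, and none if drawn on day 7. Onset concentrated earlier would raise this, to 2.6 of 9 in the most extreme pattern examined. These figures rest on the design rates, on assumed onset patterns for which the documents offer no data, and on taking the day 8 sample as the intended predictor, which is inferred from the schedule.

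Three stronger conclusions do not follow. The documents do not show that reversed timing would create the association: a shift of 0.08 in the AUC per event is a ceiling, and 0.025 to 0.04 is a fairer illustration. They do not show that two or more events will be affected, since that needs both early onset and late draws. The primary comparison of delirium incidence is not affected.

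**What to change.** In 9.3, name the day 8 (± 1) sample as the predictor. Include only patients with no DRS above 12 on or before the date of their own draw, and count as events only a first DRS above 12 after that date, up to discharge or day 30, whichever comes first. In 3.2.2, replace "the development of delirium at any point during the post-transplant hospitalization" with the same definition. State which analysis population applies.

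Ordering by date is as fine as the data allow. A DRS rating looks back over 24 hours, and no section says that clock times of draws or ratings are recorded. Same-day cases, including the day-7 case in which the sample came first, would then be left out by a stated rule.

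The cost is a sentence or two in each section, with no new visit or sample, since draws and DRS assessments are already scheduled. About one event may be lost. Delirium that began before the draw but was first detected after it will still count, so the change reduces the problem without fully removing it. The report should say so.

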9.2 Sample Size, Accrual and Duration of Accrual

For the primary objective of comparing delirium incidence between groups, a two group chi-squared test with a 0.050 one-sided significance level will have 80% power to detect the difference between a usual care proportion of 0.445 and an intervention proportion of 0.155 (odds ratio of 0.229) when the evaluable sample size in each group is 30. The anticipated rate of delirium in the control group is based on 43 – 73% incidence of delirium during hospitalization for HSCT reported in the literature. As this is the first study to evaluate the efficacy of thiamine as a prevention strategy for delirium, no data is available to generate an estimate of delirium incidence in the intervention group. However, the odds ratio (OR) hypothesized for this study is in line with other successful delirium prevention trials.^{42,43} Even if the delirium incidence in the IV thiamine group is not this low, the results of this study will provide effect sizes and 95% confidence intervals to power a future larger study.

Our sample will include 60 adult participants. UNC tumor registry records demonstrate that between 2015 and 2016 133 patients were admitted for allogeneic stem cell transplant. We estimate that we will enroll at least 50% of eligible patients, based on recruitment rates described in previous delirium intervention studies,⁴⁴ allowing us to recruit our target of 60 evaluable participants in approximately two years and complete our study in the proposed three year grant period.

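### Section 9.3 searches for a thiamine cutoff and reads its sensitivity and specificity from the same few delirium events, with no correction for the search, so the reported accuracy will be biased upward

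*Combined protocol and SAP*

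**What the plan says.** Objective 2.2.3 reads: "To determine if thiamine status is predictive of subsequent delirium onset". Endpoint 3.2.2 relates the thiamine level at the end of the intervention to delirium at any point in the post-transplant hospitalization.

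Section 9.3 gives the method. The predictor is "thiamine levels at the end of the seven day administration of thiamine". The outcome is delirium up to day 30 or discharge. One exclusion applies: "Patients who develop delirium prior to the end of the thiamine treatment will not be included in this analysis". Sensitivity and specificity are examined with ROC curves, and the plan will "attempt to find a cutoff for thiamine levels that is associated with the development of delirium".

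For this analysis 9.3 does not state a cutoff fixed in advance, a rule for choosing one, a resampling or hold-out step, a confidence interval, or whether the arms are pooled. It does not call the cutoff exploratory, and it does not call it validated.

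**The concern.** Each point on an empirical ROC curve carries sampling error. Choosing the best-looking point favours points whose error happens to be favourable. The sensitivity and specificity read at that point then include the luck that got it chosen. The fewer the events, the larger this effect, and here there are few.

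At stake is the answer to objective 2.2.3. With the plan followed exactly, the trial could report a threshold with apparently useful accuracy when thiamine carries little or no information about later delirium.

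**Working it through.** **Inputs from Section 9.2.** Delirium rates 0.445 (usual care) and 0.155 (thiamine), "when the evaluable sample size in each group is 30", one-sided alpha 0.05, stated power 80%.

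**The plan's own figure.** The mean rate is 0.30. With the usual normal approximation, z = [0.29 × √30 - 1.645 × √(2 × 0.30 × 0.70)] / √(0.445 × 0.555 + 0.155 × 0.845) = (1.588 - 1.066) / 0.615 = 0.85, so power is 0.802. The odds ratio is (0.155/0.845)/(0.445/0.555) = 0.229. Both reproduce. The plan gives no event count or precision for the thiamine analysis.

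**Events available.** 30 × 0.445 + 30 × 0.155 = 13.35 + 4.65 = 18.0 events, leaving 60 - 18 = 42 non-events. The early-delirium exclusion can only reduce the 18. If 20% are early, 18 × 0.80 = 14.4 remain; if 50%, 18 × 0.50 = 9.0. A count of 10 to 14 corresponds to an early share of 44% to 22% (1 - 10/18; 1 - 14/18).

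**Optimism, single-distribution model.** Levels are normal with SD 1 and mean 0 in non-delirious patients and -d in delirious patients, with d = √2 × Φ⁻¹(AUC). The cutoff c maximises J in the sample. Apparent J is compared with the true J of that same cutoff, Φ(c + d) - Φ(c). There are 42 non-events and 4,000 simulated trials per setting; each range runs from 10 to 14 events.

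| True AUC | Mean apparent J | Mean true J at the chosen cutoff | Ratio |
|---|---|---|---|
| 0.50 | 0.197 to 0.175 | 0 | none |
| 0.55 | 0.254 to 0.226 | 0.055 | 4.6 to 4.1 |
| 0.60 | 0.308 to 0.284 | 0.117 to 0.119 | 2.6 to 2.4 |
| 0.65 | 0.368 to 0.344 | 0.184 to 0.187 | 2.0 to 1.8 |
| 0.70 | 0.430 to 0.412 | 0.255 to 0.258 | 1.7 to 1.6 |
| 0.75 | 0.498 to 0.478 | 0.331 to 0.335 | 1.5 to 1.4 |
| 0.80 | 0.568 to 0.550 | 0.412 to 0.416 | 1.4 to 1.3 |

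The ratio varies widely, but the absolute excess in J is fairly stable: from 0.550 - 0.416 = 0.13 to about 0.20. With 12 events and no association, apparent J reaches 0.30 or more in about 14% of trials.

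**On the scale the plan names.** The average of sensitivity and specificity is (1 + J)/2. At AUC 0.65 with 12 events, J is 0.352 apparent and 0.185 true, so the averages are 0.676 and 0.593, a gap of about 8 points.

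**Arms fully separated.** Treatment may push the two arms' levels apart. At the design rates, arm alone then gives J = 13.35/18 - 16.65/42 = 0.742 - 0.396 = 0.345. Simulating that case with about 10 to 14 events gives apparent J of 0.41 to 0.52 against true J of 0.28 to 0.36, a ratio of 1.4 to 1.6.

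**Does the result depend on the exclusion?** With all 18 events kept, mean apparent J is 0.16 against 0 at AUC 0.50, and 0.335 against 0.189 at AUC 0.65. At the upper literature incidence in 9.2 (73%) with the design odds ratio, the thiamine rate is 0.382 and the total 30 × (0.73 + 0.382) = 33.4 events, or 26.7 to 20.0 after a 20% to 40% exclusion. With 20 to 27 events and 27 non-events, mean apparent J is 0.17 to 0.15 with no association, and about 0.33 against 0.19 at AUC 0.65.

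**The case against.** The strongest reply is that the size is not determined by the documents. That is correct, and it limits four stronger readings.

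- A reader might infer that the cutoff will look twice as good as it is. That holds only for J at a true AUC near 0.65, a value the documents do not support. The plan speaks of sensitivity and specificity and names no Youden rule; on the averaged scale the gap at that AUC is about 8 points.
- A reader might take 10 to 14 as the trial's event count. It rests on an assumed early share of 44% to 22%, and the upper cited incidence gives about 20 to 27.
- A reader might infer that the cutoff is meant to set entry to a later trial. The remark in 9.2 about a future larger study concerns delirium incidence and its effect size. Section 9.3 speaks only of an attempt to find a cutoff, 9.1 does not list thiamine among the secondary endpoints, and 8.5 describes a Phase II study gathering preliminary data.
- A reader might want the assaying laboratory's lower reference limit as the main cutoff. The documents give no such figure. Sections 1.2 and 1.5 cite deficiency in 100% of HSCT patients. On that premise most placebo patients may fall below the limit and most treated patients above it. The limit would then discriminate little within an arm and largely mirror arm when pooled.

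It is also fair that a single pooled normal model sits awkwardly with an intervention that raises thiamine in one arm; the separated-arms case answers that, with a smaller ratio. None of this removes the bias. It was upward in every setting computed.

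**Conclusion.** The concern holds as a matter of direction, with a size that depends on assumptions. Accuracy at the searched cutoff will be biased upward for secondary objective 2.2.3. With normal levels, a Youden rule, 10 to 14 events and 42 non-events, apparent J is overstated about 1.3 to 2.6 times for a true AUC of 0.80 to 0.60, and more for weaker associations. If the arms' levels separate fully at the design rates, the factor is about 1.4 to 1.6. More events shrink the bias but do not remove it. No single multiplier, fixed event count or downstream use of the cutoff can be read from the documents. Whether the ROC analysis is pooled or within arm is a separate gap; the bias arises either way. The primary comparison and the other objectives are not touched.

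**What to change.** In Section 9.3:

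- Name the rule that selects the cutoff.
- Label the searched cutoff exploratory.
- Report its sensitivity, specificity and J after bootstrap optimism correction. In each resample, re-select the cutoff, then subtract from the apparent value the mean of (accuracy in the resample - accuracy of that cutoff in the original data).
- Give bootstrap intervals for these quantities and for the cutoff itself.

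The laboratory's reference limit may be shown beside this as a secondary, fixed comparator, but not as the main cutoff.

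The cost is a few sentences and a resampling loop, with no extra data. The reported accuracy will be less favourable. The correction is also only partial: in simulation it removed roughly half to two thirds of the optimism in most settings, so the exploratory label must stay even after correction.
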